5.6 Dose Interruptions

Participants who have a delay in administration of a dose of the study drug of ≤ 48 hours should take the planned dose as soon as possible after the intended time of administration and continue on the same 28-day cycle (i.e., Day 15 of the same cycle will not change if Day 1 is delayed, or the next cycle start date Day 1 will not be delayed). Relevant evaluations due prior to the next sEphB4-HSA dose may be delayed accordingly.

For participants who have a delay in administration of study drug of >48 hours but ≤ 28 days (please refer back to [Sections 5.2](#), [5.3](#), and [5.5](#) for hold and stop parameters for non-hematologic and hematologic toxicities), the study drug administration may continue with the following instructions: If the Day 1 dose of any new cycle is delayed ≥ 48 hours, that cycle start date and subsequent treatment days and cycles will be reset. If the Day 15 dose of is delayed ≥ 48 hours, the following Day 1 dose of the next cycle will not be given until 14 days later. All relevant evaluations will be delayed accordingly.

Any dose interruption of more than 28 days requires discontinuation of protocol therapy.

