2.3.8 Dosing in clinical trial

A phase I trial in refractory/relapsed solid tumors has been completed. The following dose levels were tested in the phase I trial: 2.5 mg/kg, 5 mg/kg, 10 mg/kg and 15 mg/kg administered weekly on Days 1, 8, 15, and 22; and 10 mg/kg, 15 mg/kg and 20 mg/kg administered every 14 days (2 weeks) on Days 1 and 15, by I.V. infusion for 60 minutes. The weekly dosing schema and schedule was chosen based on safety of weekly dosing in animal studies of doses up to 30 mg/kg. No DLTs were seen in this weekly dosing, however dose accumulation was noted. Cohorts consisting of 10 mg/kg, 15 mg/kg and 20 mg/kg, with administration every 14 days (2 weeks), were added to the phase I trial, given the dose accumulation noted with weekly dosing. The phase I maximum tolerated dose (MTD) has been reached with 2 of 6 participants, at 20 mg/kg administered every 14 days,

experiencing grade III hypertension that was not responsive to therapy, requiring dose reduction to 15 mg/kg every two weeks, and long half-life of 7 - 10 days. Therefore, the dose of 15 mg/kg every 2 weeks, administered on Days 1 and 15, was initially used as the starting dose in this Phase II trial.³¹

Based on updated data (unpublished communication with VasGene, 8/2018) from other trials with sEphB4-HSA (ClinicalTrials.gov ID NCT03146871), which take into consideration rates of hypertension and drug accumulation, other trials have been modified to use a dose of sEphB4-HSA of 10 mg/kg every 2 weeks. Based on this information combined with initial experience in this study, this trial is amended with protocol version 4.0 to use a dose of 10 mg/kg every 2 weeks, administered on Days 1 and 15 of each cycle. In addition, other unpublished studies (ClinicalTrials.gov ID NCT02717156 and NCT03049618), which dosed sEphB4-HSA at 10 mg/kg weekly, showed grade 3/4 hypertension in 3/21 and 3/19 participants, respectively. Given the updated information of drug accumulation in the context of an approximately 5-day half-life of sEphB4-HSA, the weekly dose will not be used in this trial.

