2.5.1.1 Trough sEphB4-HSA levels

Pre-dose blood levels will be drawn on Days 1 and 15 of Cycles 1 and 2. sEphB4-HSA levels will be measured via ELISA by [name] at USC Norris Hospital.

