10.4 Analysis of Secondary Endpoints

Descriptive statistics and graphical displays will be used to evaluate correlation between response and trough levels and pharmacodynamics of sEphB4-HSA. Depending on the number enrolled, the association between clinical response and changes in trough levels, pharmacodynamic endpoints, including indicators of changes in VEGF-Notch-EphrinB2 angiogenic pathway, viral copy number, protein expression and activation status, and finally immune cell counts, and activation status will be investigated using the nonparametric Wilcoxon rank sum test.

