Urinalysis		X	X ^w		X ^w				X		
Peripheral blood sEphB4-HSA levels (see Appendix II)			X (predose and immediately prior to end of infusion)	X (predose)	X ⁿ (predose)		X ⁿ (predose)				
Peripheral blood (for immune studies) (see Appendix III)		X ^{k, z}	X ^{k, z} (predose)	X	X ^o (predose)						
Peripheral blood (for PBMCs for Research) (see Appendix III)		X ^{k, y}	X ^{k, y} (predose)	X	X ^{aa} (Cycle 4, 7, 10 only)				X		
5-mm KS Biopsy (formalin-fixed), and 5-mm KS Biopsy (RNA later)		X ^k	X ^k (predose)	X ⁱ (after Day 15 dose)							
Chest X-ray ^f , CT Scan ^p		X ^b									
ACSR Donation (Screening or Day 1, optional with consent)		X ^j									

^a To be done any time prior to study enrollment

^b To be done ≤ 28 days prior to study enrollment

^c To be done ≤ 14 days prior to study enrollment

^d To be done ≤ 7 days prior to study enrollment

^e Pregnancy test to be done on females of childbearing potential

^f Participants with a positive CXR or minimal symptoms suggestive of pulmonary involvement of KS will have a CT thorax performed. CXR not required if a thoracic CT has been performed

^g Baseline assessments can be done on Day 1, or < 14 days prior to first dose of study drug

^h Labs may be done up to 7 days prior to days 1 and 15 of each cycle; interval history and physical exam must be done up to 7 days prior to study agent administration.

ⁱ To be done after Cycle 1, Day 15 dosing. Can be done any time after treatment on Cycle 1, Day 15 and before treatment of Cycle 2, Day 1

^j To be done at any time from time of study enrollment to Day 1, if the participant consents

^k To be completed within 14 days prior to Cycle 1, Day 1 of study drug. Baseline and Day 1 can be the same day

- ¹ Baseline and Day 1 can be the same (as long as done within 4 weeks of treatment)
- ^m To be administered anytime between Cycle 4, Day 15 and Cycle 5, Day 15
- ⁿ After Cycle 1, pre-dose blood for sEphB4-HSA trough levels only to be drawn days 1, 15 of Cycle 2.
- ^o Only on Day 1 of Cycles 2, 4, and 6; to be done before study treatment dosing. Given this will be a fresh blood sent at room temperature overnight, if the blood for immune studies cannot be collected on Monday-Wednesday (i.e., the dose is administered on Thursday or Friday), this blood work can be obtained the Monday AFTER the dose was given.
- ^p Only needed if symptomatic or specific findings on CXR
- ^q To be done within 24 hours of first dose of study drug

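### Trough samples move with a held dose, so levels drawn up to 42 days after the last dose would be analysed as 14-day troughs, probably weakening the exposure-response analysis

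*Combined protocol and SAP*

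**What the plan says.** Secondary objective 1.2.2 is to determine trough exposure and relate it to tumor response. Section 2.5.1.1 fixes the samples: "Pre-dose blood levels will be drawn on Days 1 and 15 of Cycles 1 and 2". Appendix I confirms that sampling then ends: "After Cycle 1, pre-dose blood for sEphB4-HSA trough levels only to be drawn days 1, 15 of Cycle 2". Sections 8.2.1.12 and 8.2.2.11 and Appendices II and X use the same pre-dose definition. None gives a window in time since the previous dose.

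Section 5.6 sets what happens when a dose slips. For delays of 48 hours or less, "Relevant evaluations due prior to the next sEphB4-HSA dose may be delayed accordingly", and the calendar stays as it was. For delays of more than 48 hours and up to 28 days, the schedule is reset and "All relevant evaluations will be delayed accordingly". The limit is 28 days: "Any dose interruption of more than 28 days requires discontinuation of protocol therapy".

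Section 10.4 first plans descriptive statistics and graphs relating response to trough levels. Then, if numbers allow, it plans a Wilcoxon rank sum test of the "association between clinical response and changes in trough levels". It names no reference visit for the change and makes no adjustment for time since dosing.

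Section 2.3.8 gives two half-lives: "long half-life of 7 - 10 days" from the phase I trial, and later an "approximately 5-day half-life of sEphB4-HSA".

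**The concern.** A trough is comparable between participants only if it is taken at the same time after the last dose. Here the sample is tied to the act of dosing, so a hold lengthens the interval and the drug keeps clearing. The plan as written would record the resulting level as a trough.

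The error need not be random. Many holds follow toxicity, and Section 5.4 requires one for grade 3 hypertension. Section 2.3.8 links hypertension to dose and accumulation across dose levels and schedules. If the same link holds between participants at one dose, those with the highest exposure are the likeliest to be held and to record a falsely low level.

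At stake is objective 1.2.2, the only analysis in Section 10.4 that relates drug level to response. A correctly timed sample that was not drawn cannot be recovered later.

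**Working it through.** **Plan's own figures.** The documents give none for the trough analysis. The only stated error rates belong to the primary design in Section 10.2, and they reproduce. Power is P(at least 9 responders of 20 at 0.60) × P(at most 3 toxicities of 20 at 0.10) = 0.9435 × 0.8670 = 0.818, stated as 0.82. The significance level is the larger of 0.1133 and 0.1071, stated as 0.11. Nothing below alters them.

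**Inputs.** Planned interval 14 days (dosing on Days 1 and 15 of a 28-day cycle). Longest hold 28 days (Section 5.6). Half-life t of 5, 7 or 10 days (Section 2.3.8). Longest interval to a recorded trough: 14 + 28 = 42 days. Only holds at Cycle 1 Day 15, Cycle 2 Day 1 or Cycle 2 Day 15 matter, because the Cycle 1 Day 1 sample precedes any drug.

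**Step 1: the held visit.** With first-order decay, recorded level / 14-day trough = 2^(−d/t) for an extra delay of d days.

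| Delay d | t = 5 d | t = 7 d | t = 10 d |
|---|---|---|---|
| 2 days | 76% | 82% | 87% |
| 7 days | 38% | 50% | 62% |
| 14 days | 14% | 25% | 38% |
| 28 days | 2% | 6% | 14% |

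**Step 2: later visits.** Let r = 2^(−14/t), which is 0.144, 0.250 and 0.379. Take a 14-day hold at Cycle 1 Day 15 with no dose reduction.
- Cycle 2 Day 1, held / unheld = (1 + r²)/(1 + r) = 0.89, 0.85, 0.83.
- Cycle 2 Day 15, held / unheld = (1 + r + r³)/(1 + r + r²) = 0.98, 0.96, 0.94.

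The distortion sits mainly at the held visit.

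**Step 3: change between troughs.** With no hold, Cycle 2 Day 15 / Cycle 1 Day 15 = 1 + r + r² = 1.16, 1.31, 1.52. This ratio depends on half-life, not on the level of exposure. If Cycle 1 Day 15 was held 14 days, the recorded ratio becomes (1 + r + r³)/r = 8.0, 5.1, 3.8. A hold at the reference visit inflates the change, whereas a hold at the later visit lowers it. With no reference visit named, the direction of the bias is not fixed.

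**Step 4: effect on the Wilcoxon comparison of levels.** This was simulated as concordance, the probability that a responder's level exceeds a non-responder's. Inputs that are not in the documents: between-participant exposure CV 30-50%, log-odds of response 0.5-1.0 per SD of log exposure, and holds more likely at higher exposure. As a guide to frequency, Section 2.3.8 reports grade 3/4 hypertension in 3/21 (14.3%) and 3/19 (15.8%) on weekly 10 mg/kg, or about 3 of 20.
- N = 20, 3-4 held: average concordance falls from 0.63-0.64 to 0.56-0.62 (weaker link) or from 0.74 to 0.60-0.71 (stronger link). The sign flips from positive to negative in about 4-23% of trials.
- N = 20, about 7 held: the sign flips in about 7-36%.
- Large sample, 15% held: 0.53-0.68, weakened but still positive.
- Large sample, reversal (0.42-0.49): only with about 30-40% held and an exposure-toxicity correlation of 0.8 or more, mostly at the 5- or 7-day half-life.

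**The case against.** The strongest reply has five parts.

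**Late drawing is inferred.** Section 5.6 does not name the drug-level tube, and blood pressure is taken before drug administration, so blood may already have been drawn when a hold is decided. This is fair as a description of some visits. But the sample is defined as pre-dose and the instruction covers all relevant evaluations, so a site following the text would redraw or delay it, and sites may differ.

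**Long holds are limited.** Under Section 5.4 a hypertension hold that reaches 4 weeks ends treatment. Under Section 5.5 thrombocytopenia or neutropenia unresolved at 14 days does too. Grade 2 hypertension causes no hold, and grade 3 is rechecked every 3-5 days. This stands: the 28-day row is a boundary case, and 7- and 14-day holds are the more useful guide. The 14-16% hypertension rate comes from weekly dosing and may be too high here, although it counts hypertension alone.

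**The exposure-toxicity link is unproven for individuals.** This stands. Section 2.3.8 compares doses and schedules, and Section 5.4 points to baseline blood pressure and cardiac risk factors.

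**Section 10.4 already looks at levels, and change has its uses.** Its first sentence covers trough levels descriptively, so only the formal test is confined to change. Section 2.3.6 reports falling levels in monkeys with anti-drug antibodies, which a change between troughs could detect. Both points stand, and change is worth keeping as a description.

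**The consequence is modest.** The analysis is secondary and largely descriptive, Section 2.5 calls the correlative studies exploratory, and no decision rule uses it. Collection time is on the label (Appendix X), so late samples could be set aside at analysis. That is true, but setting them aside leaves no correctly timed value in their place.

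**Conclusion.** The point holds as a timing defect in a secondary analysis. As written, a level drawn up to 42 days after dosing counts as a trough. At the held visit it is about 38-62% of the proper value after 7 days' delay and 14-38% after 14, assuming first-order decay and a half-life of 5-10 days. Later troughs keep about 83-98% of their value in the case worked above.

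A reader might infer that the analysis will reverse direction. The documents do not support that. At a hold rate near their own hypertension figures, the expected effect is weakening toward no association. Reversal occurs in a minority of simulated 20-participant trials, under assumed exposure variability and an assumed individual link between exposure and toxicity. Nor is the bias always downward: change measured from a held Cycle 1 Day 15 sample is biased upward.

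The change is worth making because the loss is avoidable and cannot be fully repaired afterwards. The primary endpoint and its error rates are untouched.

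**What to change.** - **Sections 2.5.1.1 and 5.6, Appendices I, II and X:** exempt the sEphB4-HSA level from the delay. Draw it at the scheduled visit, 14 ± 2 days after the previous dose, whether or not the dose is then given.
- **Section 10.4, definition:** count a sample as a trough only if it was drawn 12-16 days after the previous dose, using the recorded collection time and the dosing record. The window matches the shifts of up to 48 hours that Section 5.6 allows without moving the calendar.
- **Section 10.4, test:** apply the Wilcoxon test to the trough level itself, for example Cycle 2 Day 15 or the last valid trough. Keep change between troughs as a descriptive addition with a named reference visit.

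**Cost.** A wording amendment, with no added assays and no change to any dosing or hold rule. A few late samples would no longer count as troughs, and a dose held before the visit may need the draw kept on its planned day. Some timing error remains inside the window: relative to 14 days, a sample at 16 days reads 76-87% and one at 12 days reads 2^(2/t) = 115-132%.

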6.0 ADVERSE EVENTS: LIST AND REPORTING REQUIREMENTS

Adverse event (AE) monitoring and reporting is a routine part of every clinical trial. The following list of AEs ([Section 6.1](#)) and the characteristics of an observed AE ([Section 6.2](#)) will determine whether the event requires expedited (via CTEP-AERS) **in addition** to routine reporting (via Advantage eClinical).

The CTEP Version 5.0 of the NCI Common Terminology Criteria for Adverse Events (CTCAE) will be utilized for AE reporting beginning April 1, 2018. The CTEP Version 5.0 of the CTCAE is identified and located on the CTEP website at

http://ctep.cancer.gov/protocolDevelopment/electronic_applications/ctc.htm.

All appropriate treatment areas should have access to a copy of the CTEP Version 5.0 of CTCAE.

This study will be monitored by the Clinical Data Update System (CDUS). Cumulative CDUS data will be submitted quarterly to CTEP by electronic means. Reports are due January 31, April 30, July 31, and October 31.

6.1 Comprehensive Adverse Events and Potential Risks Lists

6.1.1 Adverse event list for sEphB4-HSA

Agent not supplied by CTEP: Please see the investigational brochure for the full details of potential risks.

Table 6-A: sEphB4-HSA expected toxicities:

System Organ Class	Adverse Event Term
General disorders and administration site conditions	Fatigue
Nervous system disorders	Headache
Vascular disorders	Hypertension

Table 6-B: Reported on trials using sEphB4-HSA but with the relationship to sEphB4-HSA still undetermined:

System Organ Class	Adverse Event Term
Gastrointestinal disorders	Nausea
	Vomiting
	Other (hematemesis)
General disorders and administration site conditions	Chills
	Vomiting
	Fever
Neoplasms, benign, malignant and unspecified (incl. cysts and polyps)	Tumor pain
Nervous system disorders	Syncope

Table 6-C: Risks not reported in prior trials of sEphB4-HSA but the occurrence of which will be monitored in this investigation:

System Organ Class	Adverse Event Term
Blood and lymphatic system disorders	Anemia
	Leukocytosis
Cardiac disorders	Left ventricular systolic dysfunction
	Ventricular arrhythmia
	Myocardial infarction
General disorders and administration site conditions	Infusion related reaction
Immune system disorders	Allergic reaction
Investigations	Platelet count decreased
	White blood cell decreased
	Lymphocyte count increased
Metabolism and nutrition disorders	Acidosis
	Tumor lysis syndrome
	Hyperkalemia
	Hyperuricemia
	Hyperphosphatemia
	Hypocalcemia
Musculoskeletal and connective tissue disorders	Arthralgia
	Generalized muscle weakness
	Myalgia
	Myositis
Nervous system disorders	Stroke
	Ischemia cerebrovascular
	Seizure
	Tremor
Renal and urinary disorders	Acute kidney injury
	Proteinuria
Respiratory, thoracic, and mediastinal disorders	Dyspnea
Skin and subcutaneous tissue disorders	Pruritus
	Rash
Vascular disorders	
	Hypotension
	Thrombosis

Note: sEphB4-HSA in combination with other agents could cause an exacerbation of any AE currently known to be caused by the other agent, or the combination may result in events never previously associated with either agent.

6.2 Classification of AEs by Severity and Relationship to Study Drug Administration

- 6.2.1 Adverse Event: Any unfavorable and unintended sign (including an abnormal laboratory finding), symptom or disease temporally associated with the use of a medical treatment or procedure regardless of whether it is considered related to the medical treatment or procedure (attribution of unrelated, unlikely, possible, probable, or definite).
- 6.2.2 Life-threatening Adverse Event: Any AE that places the participant or participant, in view of the Investigator, at immediate risk of death from the reaction.
- 6.2.3 Serious Adverse Event (SAE): Any AE occurring at any dose that results in any of the following outcomes: Death, a life-threatening AE, inpatient hospitalization or prolongation of existing hospitalization, a persistent or significant disability/incapacity, or a congenital anomaly/birth defect.
- 6.2.4 Please note for hospitalization – All hospitalizations (or prolongation of existing hospitalization) for medical events equivalent to CTCAE grade 3, 4, 5 must be reported regardless of the requirements for Phase of study, expected or unexpected, and attribution. For example, do not report an admission for pharmacokinetic sampling, but do report an admission for a myocardial infarction.
- 6.2.5 Toxicity: Toxicity is a term NOT clearly defined by regulatory organizations. Toxicity has been described as an AE that has an attribution of possibly, probably or definitely related to investigational treatment. To minimize confusion the NCI would recommend that the term toxicity NOT be utilized for AE reporting purposes. The CTCAE continues to use the term ‘toxicity’ because of familiarity.
- 6.2.6 Unexpected Adverse Event: Any AE that is not listed in available sources including the package insert, the Investigator’s Brochure, or the protocol.
- 6.2.7 CTEP Adverse Event Reporting System (CTEP-AERS): An electronic system for expedited submission of AE reports.
- 6.2.8 Attribution: The determination of whether an AE is related to a medical treatment or procedure. Attribution categories:
 - Definite – The AE is clearly related to the investigational agent.
 - Probable – The AE is likely related to the investigational agent.
 - Possible – The AE may be related to the investigational agent.
 - Unlikely – The AE is doubtfully related to the investigational agent.
 - Unrelated – The AE is clearly NOT related to the investigational agent.

6.3 Expedited Adverse Event Reporting

- 6.3.1 Expedited AE reporting for this study must use CTEP-AERS (CTEP Adverse Event Reporting System), accessed via the CTEP home page (<http://ctep.cancer.gov>). The reporting procedures to be followed are presented in the “CTEP, NCI Guidelines: Adverse Event Reporting Requirements” which can be downloaded from the CTEP

home page (<http://ctep.cancer.gov>). These requirements are briefly outlined in the table below ([Section 6.3.3](#)).

A 24-hour notification is to be made to AMC ODMC by telephone at [contact], only when Internet connectivity is disrupted. Once Internet connectivity is restored, a 24-hour notification phoned in must be entered electronically into CTEP-AERS by the original submitter at the site.

- 6.3.2 CTEP-AERS is programmed for automatic electronic distribution of reports to the following individuals: Study Coordinator of the Lead Organization, Principal Investigator, and the local treating physician. CTEP-AERS provides a copy feature for other email recipients.

- 6.3.3 Expedited reporting guidelines

All unacceptable toxicities should be reported no later than the end of the current cycle.

Use the NCI protocol number and the protocol-specific participant ID assigned during trial registration on all reports.

Note: A death on study requires both routine and expedited reporting regardless of causality, unless as noted below. Attribution to treatment or other cause must be provided.

Death due to progressive disease should be reported as **grade 5 “General disorders and administration site conditions – Disease Progression”** under the system organ class (SOC) of the same name. Evidence that the death was a manifestation of underlying disease (e.g., radiological changes suggesting tumor growth or progression: clinical deterioration associated with a disease process) should be submitted.

Table 6-D: Phase 1 and early phase 2 studies: Expedited reporting requirements for adverse events that occur on studies under an IND/IDE within 30 days of the last administration of the investigational agent/intervention ^{1, 2}

FDA REPORTING REQUIREMENTS FOR SERIOUS ADVERSE EVENTS (21 CFR Part 312)

NOTE: Investigators **MUST** immediately report to the sponsor (NCI) **ANY** Serious Adverse Events, whether or not they are considered related to the investigational agent(s)/intervention (21 CFR 312.64)

An adverse event is considered serious if it results in **ANY** of the following outcomes:

- Death
- A life-threatening adverse event
- An adverse event that results in inpatient hospitalization or prolongation of existing hospitalization for ≥ 24 hours
- A persistent or significant incapacity or substantial disruption of the ability to conduct normal life functions
- A congenital anomaly/birth defect.

Important Medical Events (IME) that may not result in death, be life threatening, or require hospitalization may be considered serious when, based upon medical judgment, they may jeopardize the participant or participant and may require medical or surgical intervention to prevent one of the outcomes listed in this definition. (FDA, 21 CFR 312.32; ICH E2A and ICH E6).

ALL SERIOUS adverse events that meet the above criteria **MUST** be immediately reported to the NCI via CTEP-AERS within the timeframes detailed in the table below.

Hospitalization	Grade 1 and Grade 2 Timeframes	Grade 3-5 Timeframes
Resulting in Hospitalization ≥ 24 hrs	10 Calendar Days	24-Hour 5 Calendar Days
Not resulting in Hospitalization ≥ 24 hrs	Not required	

NOTE: Protocol specific exceptions to expedited reporting of serious adverse events are found in the Specific Protocol Exceptions to Expedited Reporting (SPEER) portion of the CAEPR.

Expedited AE reporting timelines are defined as:

- “24-Hour; 5 Calendar Days” - The AE must initially be reported via CTEP-AERS within 24 hours of learning of the AE, followed by a complete expedited report within 5 calendar days of the initial 24-hour report.
- “10 Calendar Days” - A complete expedited report on the AE must be submitted within 10 calendar days of learning of the AE.

¹Serious adverse events that occur more than 30 days after the last administration of investigational agent/intervention and have an attribution of possible, probable, or definite require reporting as follows:

Expedited 24-hour notification followed by complete report within 5 calendar days for:

 All Grade 3, 4, and Grade 5 AEs

Expedited 10 calendar day reports for:

 Grade 2 AEs resulting in hospitalization or prolongation of hospitalization

² For studies using PET or SPECT IND agents, the AE reporting period is limited to 10 radioactive half-lives, rounded UP to the nearest whole day, after the agent/intervention was last administered. Footnote “1” above applies after this reporting period.

Effective Date: May 5, 2011

